14.4.3 Reporting Results

The least squares (LS) mean of CFB in blood bicarbonate, standard error (SE) of the LS mean, two-sided 95% CI of the LS mean, and p-value from the mixed model will be reported by treatment group and time point. The LS mean difference of the CFB in blood bicarbonate between the TRC101 group and the placebo (i.e., TRC101 – placebo), SE of the LS mean difference, 95% CI of the LS mean difference, and the p-value of the LS mean difference from the mixed model will be provided by time point.

In addition, descriptive statistics for blood bicarbonate at baseline and at each scheduled post-baseline time point, along with CFB in blood bicarbonate, will be summarized by treatment and time point. Graphs will be produced to show:

- LS mean \pm 95% CI of change from baseline in blood bicarbonate (from the mixed model) by treatment group over time
- Arithmetic mean \pm SE of change from baseline in blood bicarbonate (from descriptive statistics) by treatment group over time
- LS mean \pm 95% CI of blood bicarbonate (from the mixed model) by treatment group over time
- Arithmetic mean \pm SE of blood bicarbonate (from descriptive statistics) by treatment group over time

14.4.4 Statistical Testing

Using the above described mixed model (Section 14.4.2), $LS\ mean_{TRC101} = LS\ mean_{placebo}$ at the Week 12 Visit will be formally tested for statistical significance, only when the primary efficacy endpoint is statistically significant. In order to maintain the family-wise error rate, a statistically significant TRC101 effect (LS mean difference >0) will be declared if the two-sided p-value at Week 12 is <0.05 and the primary efficacy endpoint is statistically significant.

14.5 Sensitivity Analyses for Primary and Secondary Efficacy Endpoints

In order to evaluate the potential effect of missing data on the primary and secondary efficacy results, sensitivity analyses will be performed using multiple imputation models under a MNAR assumption for the MITT analysis set. We will use a multiple imputation method with Copy Reference (CR) method using estimated means in the placebo group. The method is based on the assumption that subjects who stop taking TRC101 will no longer benefit from it in the future, and thus will tend to have outcomes similar to those in the placebo group. Although the scientific justification of the method seems reasonable, it is important to note that any such sensitivity analysis still relies on untestable assumptions about unobserved data, so does ignoring the missing data as the primary outcome.

Multiple imputation inference involves the following three steps:

1. The missing bicarbonate data are filled in m times to generate m complete datasets using SAS® PROC MI based on multiple imputation method CR. We will set m to be 100.
2. The analysis methods described in Sections 14.3.1 and 14.4.2 will be applied to the m completed datasets.
3. The results from the m completed datasets are combined using SAS® PROC MIANALYZE for confirmatory of the primary and secondary efficacy analyses.

14.6 Subgroup Analyses of the Primary and Secondary Efficacy Endpoints

Subgroups defined in Section 11.10 will be used to explore the effect of the primary and secondary efficacy endpoints by intrinsic and extrinsic factors. The subgroup analyses for the primary efficacy endpoint will be analyzed as described in Section 14.3.1. The subgroup analyses for the secondary efficacy endpoint will be analyzed as described in Sections 14.4.2 and 14.4.3.

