7 STUDY DESIGN

7.1 Overall Study Design

This is a double-blind, placebo-controlled, parallel-design, 2-arm study. Approximately 210 subjects will be randomized in a 4:3 ratio to receive 6 g TRC101 or placebo once daily (QD). Approximately 55 study centers will participate in this study.

Screening Period: Eligible subjects will be enrolled into the study if they: are 18 to 85 years of age; have a blood bicarbonate value of 12 to 20 mEq/L at Screening 1 and Screening 2; have an average value of blood bicarbonate from Screening 1, Screening 2, and Day 1 pre-dose (i.e., baseline blood bicarbonate) within the 12 to 20 mEq/L range; and have an estimated glomerular filtration rate (eGFR) of 20 to 40 mL/min/1.73m² at both the Screening 1 and Screening 2 visits. Additional inclusion and exclusion criteria can be found in the TRCA-301 protocol, Section 4. Randomization of eligible subjects will be based on their baseline blood bicarbonate strata (≤ 18 versus > 18 mEq/L) and Screening eGFR strata (< 30 versus ≥ 30 mL/min/1.73m², where Screening eGFR is defined as the average of Screening Visit 1 and Screening Visit 2 values).

Treatment Period: Randomized subjects will receive study drug (placebo or TRC101) for 12 weeks (Treatment Period) on an outpatient basis. The dose of the study drug will be fixed for the first 4 weeks of the Treatment Period, except for subjects with a blood bicarbonate level ≥ 27 mEq/L. Subjects with a blood bicarbonate level of 27 to 30 mEq/L will have their dose of study drug decreased per the titration algorithm (see TRCA-301 protocol, Appendix 2). Subjects with a confirmed blood bicarbonate level of > 30 mEq/L will undergo an interruption of the study drug

dose in accordance with the titration algorithm (see TRCA-301 protocol, Appendix 2). Beginning at the Week 4 Visit, subjects with a blood bicarbonate level below the normal range (12 to < 22 mEq/L) will have an adjustment of the study drug dose in accordance with the titration algorithm (see Protocol Appendix 2). At any time during the study, subjects with a confirmed blood bicarbonate level < 12 mEq/L will be evaluated by the Investigator for new acute acidotic processes and discussed with the Medical Monitor. During the 12-week Treatment Period, subjects will attend eight study visits (Day 1, Weeks 1, 2, 4, 6, 8, 10, and 12) for efficacy and safety assessments (See Table 1 for details).

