8 SAMPLE SIZE AND POWER

8.1 Primary Efficacy Endpoint

The primary efficacy endpoint is having a change from baseline (CFB) in blood bicarbonate ≥ 4 mEq/L or having blood bicarbonate in the normal range (22 to 29 mEq/L) at the end of treatment (Week 12 Visit). This outcome is termed a “response”.

The sample size in this study is based on the efficacy results observed in the Phase 1/2 Study TRCA-101. The table below shows 46% of TRC101-treated subjects and 3% of placebo-treated subjects had an increase of ≥ 4 mEq/L or had blood bicarbonate in the normal range (22 to 29 mEq/L) after 2 weeks of treatment. We assume the full TRC101 treatment effect had not been reached during the short (2-week) treatment period.

Results from Study TRCA-101

Blood Bicarbonate (mEq/L)	Pooled TRC101 (n=104)	Pooled Placebo (n=31)
Number (%) of Subjects at Week 2 (Day 15)		
CFB ≥ 4	41 (39.4%)	1 (3.2%)
Normal (22 - 29)	37 (35.6%)	0
Composite (CFB ≥ 4 or Normal)	48 (46.2%)	1 (3.2%)
95% Exact CI of Composite	36.3%, 56.2%	<0.1%, 16.7%

CFB = Change from baseline; CI = confidence interval.

In Study TRCA-301, we expect that 50 to 55% of TRC101-treated and 10% of placebo-treated subjects will have an increase of ≥ 4 mEq/L or have blood bicarbonate in the normal range at the end of treatment (Week 12 Visit). A Fisher's exact test with a 0.05 two-sided significance level will have over 99% power to detect this difference if the study has 90 placebo and 120 TRC101 subjects. If the true proportion of TRC101 subjects who respond at the Week 12 Visit is indeed between 50% and 55% and if no more than 5% of subjects have missing data at Week 12, the study will have roughly 90% power to result in a 95% confidence limit with a lower bound of at least 35% and 40%, respectively.

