11.6 Multicenter Considerations

Thirty-seven (37) study centers in Europe and the United States randomized at least 1 subject in the study as follows: European Union (EU) countries (8 sites with 82 subjects); Non-EU countries (17 sites with 108 subjects); and the United States (12 sites with 27 subjects). Data from all study centers will be pooled for efficacy and safety analyses as well as for summaries. Because the number of subjects at each center is likely to be small, no analyses will be performed by center. Geographic region (i.e., EU, Non-EU, and US), in which study sites in certain geographic locations will be pooled together, will be used for subgroup analyses. The table below lists these study centers with their site identification number, country and geographic region category.

Table 3 Country Code and Geographic Region Category

Site Identification Number	Country Code	Country Name	Geographic Region
11	BGR	Bulgaria	EU
21	HRV	Croatia	EU
41	HUN	Hungary	EU
44	HUN	Hungary	EU
46	HUN	Hungary	EU
49	HUN	Hungary	EU
71	SVN	Slovenia	EU
72	SVN	Slovenia	EU
31	GEO	Georgia	Non-EU
32	GEO	Georgia	Non-EU
33	GEO	Georgia	Non-EU

Table 3 Country Code and Geographic Region Category

Site Identification Number	Country Code	Country Name	Geographic Region
34	GEO	Georgia	Non-EU
35	GEO	Georgia	Non-EU
36	GEO	Georgia	Non-EU
37	GEO	Georgia	Non-EU
61	SRB	Serbia	Non-EU
64	SRB	Serbia	Non-EU
65	SRB	Serbia	Non-EU
81	UKR	Ukraine	Non-EU
83	UKR	Ukraine	Non-EU
84	UKR	Ukraine	Non-EU
85	UKR	Ukraine	Non-EU
86	UKR	Ukraine	Non-EU
87	UKR	Ukraine	Non-EU
88	UKR	Ukraine	Non-EU
52	USA	United States	USA
53	USA	United States	USA
54	USA	United States	USA
55	USA	United States	USA
56	USA	United States	USA
57	USA	United States	USA
58	USA	United States	USA
59	USA	United States	USA
91	USA	United States	USA
92	USA	United States	USA
93	USA	United States	USA
95	USA	United States	USA

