14.3.1 Reporting Results

The number and proportions (expressed as percentages) of subjects who are responders at each time point and at the end of treatment will be calculated. A responder is defined as a subject who has a change from baseline in blood bicarbonate ≥ 4 mEq/L or has a blood bicarbonate in the normal range (22 to 29 mEq/L). The difference in proportion of responders between TRC101 and placebo subjects and its two-sided exact (Clopper Pearson) 95% CI, as well as the p-value from Fisher's exact test comparing the TRC101 group and the placebo group, will be reported by time point. The exact 95% CIs will also be presented by treatment group and time point.

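### Efficacy is explored by subgroup using within-row tests only; no treatment-by-subgroup result is specified, and the 27-subject US row has about a 30-48% chance of a non-significant Fisher p-value even if the effect is the same in every region

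*SAP*

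**What the plan says.** SAP 14.6 sets out to explore the primary and secondary effects by intrinsic and extrinsic factors, using the subgroups of 11.10. For the primary endpoint: "The subgroup analyses for the primary efficacy endpoint will be analyzed as described in Section 14.3.1". Section 14.3.1 reports the responder proportions by arm with exact intervals, the difference with its 95% interval, and the p-value of Fisher's "exact test comparing the TRC101 group and the placebo group". For the secondary endpoint, 14.6 points to 14.4.2 and 14.4.3. The fixed effects there are treatment, time point and their interaction, with baseline eGFR and baseline bicarbonate as covariates. There is no subgroup term.

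Section 11.10 lists eight factors. Seven are baseline characteristics, including region (EU, non-EU, US); the eighth is dose titration status. Results go into forest plots beside the overall result. Section 11.6 gives 82 EU subjects, 108 non-EU subjects and, last in its list, "the United States (12 sites with 27 subjects".

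Treatment by time point is the only interaction named in either document. SAP 11.6, 11.10, 14.6 and 14.8.4 contain no heterogeneity test, no interaction estimate and no rule for judging consistency.

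**The concern.** Whether the effect varies by region, stratum, age, sex or alkali use is a question about differences between rows. A row p-value answers another question: whether that row alone reaches significance. With a common effect, the answer depends mainly on how many subjects the row holds.

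The region rows differ four-fold in size, and the SAP gives their counts. If EU and non-EU are significant and the US is not, a reader may take this as a weaker effect in US patients. The plan has no pre-specified result that speaks to that reading. A comparison added after unblinding would carry less weight.

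**Working it through.** **Inputs**

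- Responder rates (SAP 8.1): "we expect that 50 to 55% of TRC101-treated and 10% of placebo-treated subjects".
- Test and overall power (SAP 8.1): "A Fisher's exact test with a 0.05 two-sided significance level will have over 99% power to detect this difference". The planned arm sizes in the same section are 120 on TRC101 and 90 on placebo.
- Allocation 4:3 (SAP 7.1). Region totals 82, 108 and 27 (SAP 11.6).
- Secondary endpoint (SAP 8.2): expected Week 12 changes 4.25 and 0.25, so a difference of 4.0 mEq/L; SD 3.0.
- Not in the documents: arm sizes within region. Region is not a stratification factor. The 4:3 ratio gives 27 × 4/7 = 15.4 and 27 × 3/7 = 11.6 in the US, taken as 15/12; 16/11 and 18/9 are also shown. EU: 46.9 and 35.1, taken as 47/35. Non-EU: 61.7 and 46.3, taken as 62/46.

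**1. The plan's own figure.** Exact Fisher power is the sum, over all responder counts (a, c) with two-sided p < 0.05, of Bin(a; n1, p1) × Bin(c; n2, p2). For 120 vs 90 it exceeds 99.99% at both 50% and 55% vs 10%. The stated figure of over 99% is reproduced.

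**2. Row power for the primary endpoint under a common effect**

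| Row (TRC101/placebo) | 50% vs 10% | 55% vs 10% |
|---|---|---|
| EU 47/35 | 98.0% | 99.5% |
| Non-EU 62/46 | 99.7% | >99.9% |
| US 15/12 | 60.3% | 69.9% |
| US 16/11 | 52.3% | 64.5% |
| US 18/9 | 47.3% | 60.2% |
| US, one missing: 14/12 | 54.2% | 64.3% |
| US, one missing: 15/11 | 49.5% | 60.5% |

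The chance of p ≥ 0.05 in the US is one minus these values. For 15/12 and 16/11 it runs from 30.1% (15/12, 55%) to 47.7% (16/11, 50%). At 18/9 and 50% it is 52.7%. With one of the 15/12 subjects missing it is 36-51%.

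The critical counts show why. At 15/12, one placebo responder (1.2 expected) requires at least 7 TRC101 responders, against 7.5 expected at 50%. Two placebo responders require 9.

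**3. The misleading pattern.** P(US not significant, both others significant) = (1 − US power) × EU power × non-EU power.

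- 15/12, 50%: 0.397 × 0.980 × 0.997 = 0.388
- 16/11, 50%: 0.477 × 0.980 × 0.997 = 0.466
- 15/12, 55%: 0.301 × 0.9945 × 0.9995 = 0.30 (rounded)
- 16/11, 55%: 0.355 × 0.9945 × 0.9995 = 0.353

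**4. A direct comparison between regions.** Let d_i be the risk difference in region i and w_i the inverse of its variance. Q = Σ w_i (d_i − d̄)², with d̄ the weighted mean, is referred to chi-square on 2 df. In 20,000 simulated trials with a common effect, Q was significant in 4.5-4.7%; a separate simulation of a test on adjusted risk differences gave 3.8-4.0%. If the US effect were truly nil (10% in both arms), Q would detect it in about 70% of trials (50% vs 10% elsewhere) to 81% (55% vs 10%).

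**5. The size of the US estimate.** At 15/12 and 50% vs 10%, the expected difference is 0.40. The half-width is 1.96 × √(0.25/15 + 0.09/12) = 0.305. Over the three splits and both rates, an observed difference of zero or less has probability 0.3-1.2%.

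**6. Secondary endpoint.** Approximating the Week 12 MMRM contrast by a t-test with 2 df removed for covariates, the noncentrality at 15/12 is 4.0 / (3.0 × √(1/15 + 1/12)) = 3.44, and power is 90.9%. It is 90.3% at 16/11 and 87.8% at 18/9. Non-significance is therefore about 9-12%.

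**The case against.** The analyses are exploratory. The formal testing sequence in SAP 11.7, 14.3.3 and 14.4.4 does not involve subgroups, and no decision rests on a row. The plan reports estimates with intervals and sets them beside the overall result. A reader of the forest plot would usually see a US interval that is wide but overlaps the overall estimate. P-values beside such intervals are a matter of style, and an interaction test has low power where rows are small. All of this stands, and it limits the importance of the point. It does not supply the missing comparison: p-values are specified, and none addresses the stated aim.

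Three stronger readings are tempting and are not supported.

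- That the US row will probably look like no effect. At a split near 4:3 with complete data, a significant US Fisher result is more likely than not (52-70%), and an observed difference near zero would be rare.
- That the plan judges subgroups by significance. No section says so.
- That small rows will end up with MMRMs that cannot be compared. Seven visits imply 7 × 8/2 = 28 covariance parameters, and 14.4.2 allows simpler structures if the unstructured fit fails. But 27 subjects can give up to 189 observations, and the frequency of non-convergence has not been quantified. Separate fits per row are the natural reading of 14.6 but are not stated in words.

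**Conclusion.** The gap is real and modest. The plan explores effect variation with within-row results only. For the primary endpoint, under one common effect, the US Fisher row would be non-significant in roughly 30-48% of trials while the other two regions are almost certain to be significant. A direct region comparison would mislead in about 4-5%. For the secondary endpoint the corresponding US risk is about 9-12%.

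These figures assume that the planned rates, Week 12 difference and SD apply in the US, and that the US split is 15/12 or 16/11 with complete data. An 18/9 split raises the primary risk to about 53% at the 50% rate, and one missing subject can raise it to about 51%. The primary analysis and its error control are not affected.

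**What to change.** In SAP 14.6, for each of the seven baseline factors in 11.10, keep the row estimates with 95% confidence intervals and add one exploratory treatment-by-subgroup result from the full MITT set:

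- Primary endpoint: a test of equal risk differences across rows, or a logistic treatment-by-subgroup interaction.
- Secondary endpoint: a single MMRM with a common covariance and a treatment-by-subgroup-by-visit term (with its lower-order terms), read at Week 12. This also removes any doubt about different covariance structures between rows.

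State that consistency is judged by this result together with the row intervals, not by row p-values. Dropping the row p-values is optional. Titration status is not a baseline factor and is outside this change.

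The cost is SAP wording and a little programming, to be settled before unblinding. The interaction result will have low power for small rows, so a non-significant one must not be read as proof of consistency; the wide row interval will show that limit.

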14.7 Exploratory Efficacy Analyses - KDQOL and Repeated Chair Stand Test

The exploratory efficacy variables, the total score of the KDQOL Question 3 items (daily activities) and the repeated chair stand test duration (time, in seconds, to complete five stands), will be collected at baseline and once at the Week 12 Visit or early termination; ANCOVA models will be used for the analyses. The KDQOL Short Form (version 1.3) Question 3 individual item scores (i.e., item a-j) will be transformed as described in the KDQOL Short Form scoring manual

(Hays, 1997). Scores of 1, 2, and 3 will be recoded to 0, 50, and 100, respectively. The total score of the KDQOL Question 3 items is defined as the average of recoded item (i.e., item a-j) scores. The ANCOVA models will comprise the CFB value (i.e., total score of the KDQOL Question 3 items [daily activities] or repeated chair stand test duration, accordingly) as the dependent variable; treatment group as a fixed effect; and the baseline value, the baseline eGFR, and baseline blood bicarbonate as continuous covariates. The LS mean of CFB values, SE of the LS mean, two-sided 95% CI of the LS mean, and p-value from the ANCOVA model will be reported by treatment group. The LS mean difference of the CFB values between the TRC101 group and the placebo (i.e., TRC101 – placebo), SE of the LS mean difference, 95% CI of the LS mean difference, and the p-value of the LS mean difference will also be provided.

Individual items of the KDQOL Question 3, the total score, and change from baseline in total score will be presented in a subject listing. Repeated chair stand time to complete five stands, change from baseline in duration, reason for failed test, single chair stand result (with or without help, without or without using arm to stand) will be provided in subject listing.

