6.6 Repeated Chair Stand Test

The Investigator or qualified designee will administer the repeated chair stand test ([Guralnik; 1995](#)) at the time points indicated in the Schedule of Events (Appendix 1). The repeated chair stand test at the Screening 1 Visit will be performed for subject's training purposes only, without collecting the data. The repeated chair stand test in this study will be used as a measure of lower extremity muscle strength. Site staff will be trained to perform the testing in a consistent manner. The procedure details are provided in the Study Reference Manual.

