8.5.2 Efficacy Endpoints

Primary Efficacy:

Having a CFB in blood bicarbonate ≥ 4 mEq/L or having a blood bicarbonate in the normal range (22 to 29 mEq/L) at the end of treatment (Week 12 Visit).

Secondary Efficacy:

CFB in blood bicarbonate at the end of treatment (Week 12 Visit).

Exploratory Efficacy:

1. CFB in the total score of the KDQOL Question 3 items (daily activities) at the end of treatment (Week 12 Visit).
2. CFB in repeated chair stand test duration at the end of treatment (Week 12 Visit).

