10.2 Analysis Windows

Clinical visits may occur outside protocol-specified windows. Therefore, instead of relying solely on visit labels in the clinical database, analysis visits and their windows are defined using Study Day (See Section 10.1.2). For the purposes of data analysis and summary, assessments and/or measurements will be flagged based on the collection date/time that is closest to the protocol-scheduled time point (or target Study Day). Analysis visit windows are presented in Table 2 by type of assessments and/or measurements.

Table 2 Analysis Visit Windows

Protocol Scheduled Time Point	Target Study Day	Analysis Visit Windows (Study Day)					
		All Other Assessments	Hematology Urinalysis Spot Urine Pregnancy Tests	Repeated Chair Stand KDQOL Biomarkers	24-Hour Urine Collection	ECG	Body Weight
Screening 1	-14	$\leq -8^*$	$\leq -8^*$	-	-	-	-
Screening 2	-1	-7 to -1*	-	-	-	-	-
Day 1	1	1*	-7 to 1*	-14 to 1*	-14 to 1*	-	$\leq 1^*$
Week 1	8	2 to 11	-	-	-	-	-
Week 2	15	12 to 22	-	-	-	2 to 28	-
Week 4	29	23 to 36	-	-	-	-	2 to 42
Week 6	43	37 to 50	2 to 63	-	-	29 to 63	-
Week 8	57	51 to 64	-	-	-	-	43 to 70
Week 10	71	65 to 78	-	-	-	-	-
Week 12	85	79 to 90	64 to 91	≥ 2	64 to 91	71 to 91	-
Week 13	92	91 to 97	-	-	-	-	-
Week 14	99	≥ 98	≥ 92	-	-	≥ 92	≥ 92

* Use visit designation for scheduled visits; otherwise use the visit window.

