11.2 Handling Dropouts or Missing Data

Missing data will not be imputed, unless otherwise specified. Early termination visits will be mapped to the next scheduled visit for inclusion in summary tables, where appropriate. For example, subjects who terminate after Week 11 (e.g., have assessments through Week 11) would have their early termination assessments mapped to the next scheduled visit (i.e. Week 12) based on the analysis window (See Section 10.2).

Every effort will be made to ensure completeness of data collection. If severity or relationship of an AE to study drug is not recorded, the severity or relationship will be imputed as “severe” or relationship as “possibly related”, for analysis purposes. In the subject listing, both collected and imputed values will be presented.

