14.8.2 Categorical Change in Blood Bicarbonate

The proportions (expressed as percentages) of subjects with increases in their blood bicarbonate by ≥ 2 , ≥ 3 , ≥ 4 , ≥ 5 , ≥ 6 , and ≥ 7 mEq/L at each time point and at the end of treatment will be reported as described in the Section 14.3.1 for MITT subjects.

14.8.3 Change from Baseline in Biomarkers at Week 12

Efficacy variables, such as parathyroid hormone, serum pre-albumin, 25-hydroxy-vitamin D, urinary biomarkers of bone resorption (NTX and CTX), serum biomarkers of bone resorption (TRAP 5b, BSAP, and P1NP), urine renal biomarkers (aldosterone, uric acid, sulfate, and ET-1), and serum osteocalcin, all collected at baseline and once post baseline (at Week 12 Visit or early termination) will be analyzed using ANCOVA models similar to those described in Section 14.7, except for UAGT. Aldosterone, uric acid, sulfate, CTX, NTX, endothelin-1, and angiotensinogen are measured in the 24-hour urine collection.

For UAGT, geometric mean and 95% CI of the geometric mean, along with n, min and max, will be presented by treatment group and time point. The ANCOVA models will comprise the natural logarithm of the post baseline UAGT value as the dependent variable; treatment group as a fixed effect; and the natural logarithm of baseline value, the baseline eGFR, and baseline blood bicarbonate as continuous covariates. The geometric LS mean and two-sided 95% CI of the geometric LS mean from the ANCOVA model will be reported by treatment group. The geometric LS mean ratio (TRC101/placebo), 95% CI of the geometric LS mean ratio, and the p-value will also be provided. The geometric (LS) mean and its 95% CI will be obtained by exponentiating the (LS) mean and 95% CI on the natural log-scale.

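### The chair-stand ANCOVA has no rule for subjects who cannot complete five stands, so the worst results drop out of this exploratory comparison

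*SAP*

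**What the plan says.** Protocol 8.5.2 lists as an exploratory endpoint "CFB in repeated chair stand test duration at the end of treatment (Week 12 Visit"). Protocol 6.6 calls the test a measure of lower-extremity strength. For how it is done, that section says: "The procedure details are provided in the Study Reference Manual".

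SAP 14.7 defines the variable as "repeated chair stand test duration (time, in seconds, to complete five stands"). It fits an ANCOVA to the change from baseline, with treatment as a fixed effect and the baseline value, baseline eGFR and baseline bicarbonate as covariates.

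The same section expects failed tests. Its subject listing will show "change from baseline in duration, reason for failed test, single chair stand result" and related items. It gives no score, cap or rank for a failed test, and no count of failures by arm.

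On missing values, SAP 11.2 says: "Missing data will not be imputed, unless otherwise specified". The one imputation that is specified, in SAP 14.5, concerns bicarbonate: "The missing bicarbonate data are filled in m times to generate m complete datasets".

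SAP 14.7 also says that the single post-baseline test is done at Week 12 or at early termination. In SAP Table 2, the Week 12 window for chair stand, KDQOL and biomarkers opens on Study Day 2 and has no upper limit.

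**The concern.** Time to complete five stands exists only for those who complete them. Inability to finish is the worst result the test can give, yet it enters the dataset as a missing number. Removing such subjects selects on the outcome after randomization.

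If TRC101 improves leg strength, more placebo than TRC101 subjects should fail, and the model loses the placebo results that would have shown the difference. If TRC101 does harm, the same mechanism hides some of it.

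Failures are plausible in this trial. Subjects may be up to 85 years old (Protocol 4.2) and may have NYHA Class III heart failure (Protocol 1.6). At stake is the reading of one of the two exploratory efficacy endpoints named in the protocol.

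**Working it through.** **No figure to reproduce.** Neither document gives a mean, SD, expected effect, failure rate or power for the chair stand.

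**Step 1: what happens to a failed test.**
- The outcome is seconds to complete five stands, so a failed test has no value (SAP 14.7).
- The default is no imputation (SAP 11.2).
- The exception in SAP 14.5 covers bicarbonate only.
- Failure and its reason are listed and do not enter the model (SAP 14.7).

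A subject who fails at baseline or at the post-baseline visit therefore has no change from baseline and is not in the ANCOVA. This is the default consequence of these sections. No section states it as a rule.

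**Step 2: illustration with faster times.** All inputs are assumptions: baseline mean 15 s, SD 5 s, residual SD 3 s, a constant treatment shift, 400,000 simulated subjects, and the slowest 2% to 15% of placebo times at Week 12 treated as failures, with the same cutoff on TRC101. Shrinkage = 1 − (estimate with Week 12 failures dropped ÷ estimate with everyone).

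| True benefit | Placebo failing | TRC101 failing | Everyone | Failures dropped | Shrinkage |
|---|---|---|---|---|---|
| 1 s | 2% | 1.3% | 1.004 s | 0.977 s | 2.7% |
| 1 s | 5% | 3.5% | 1.004 s | 0.950 s | 5.4% |
| 1 s | 10% | 7.3% | 1.004 s | 0.913 s | 9.1% |
| 1 s | 15% | 11.3% | 1.004 s | 0.884 s | 12.0% |
| 2 s | 2% | 0.8% | 1.996 s | 1.953 s | 2.2% |
| 2 s | 15% | 8.4% | 1.996 s | 1.785 s | 10.6% |

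With no true effect, the estimate after dropping failures stays within 0.005 s of zero.

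**Step 3: illustration with slower times.** Again all assumed: log baseline time normal around log 18 s with SD 0.35, log change SD 0.2 or 0.3, a treatment shift of −0.08 on the log scale (about 8%), and failure when the time exceeds 25, 30 or 40 s. Both estimates are restricted to subjects who could complete the test at baseline.

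| Cutoff | SD of log change | Failing at baseline | Week 12 failing, placebo / TRC101 | Shrinkage |
|---|---|---|---|---|
| 40 s | 0.2 | 1% | 1.6% / 0.8% | 7% |
| 40 s | 0.3 | 1% | 3.5% / 2.2% | 16% |
| 30 s | 0.2 | 7% | 5.3% / 2.9% | 15% |
| 30 s | 0.3 | 7% | 9.1% / 6.3% | 28% |
| 25 s | 0.2 | 17% | 8.9% / 5.1% | 22% |
| 25 s | 0.3 | 17% | 13.9% / 9.8% | 36% |

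Repeat runs of this set-up ranged from 6% to 37%. The largest values need about 17% of subjects to be unable to complete the test already at baseline.

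**Step 4: early-termination values.** If a share d of analysed subjects is measured at early termination, when a fraction f of the Week 12 effect is present, the difference retained is 1 − d(1 − f). As a proxy for d, take the 5% ceiling on missing Week 12 data assumed in SAP 8.1. With f = 0 this gives 1 − 0.05 × 1 = 95%. With f = 0.5 it gives 1 − 0.05 × 0.5 = 97.5%.

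**The case against.** **The exclusion is inferred.** It follows from silence plus the no-imputation default, and the Study Reference Manual is not among the documents. That is fair. But the protocol cites the manual for the procedure, and neither document gives another way for a failed test to enter the analysis.

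**Failures are not hidden, and the endpoint is exploratory.** Both points are true. A listing by subject is still not a comparison by arm, and it leaves the scoring of failures to be chosen after unblinding.

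**The size rests on assumptions.** It does. The larger figures need frequent failure, and there would be little bias if few subjects fail. The direction could also differ if inability to finish is not simply an extension of slow times.

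**A reader might also infer that the Day 2 opening distorts the Week 12 comparison.** The documents do not support that. SAP 14.7 and 14.8.3 openly include early-termination values. SAP 10.2 selects the record closest to the target day, so a subject tested near Day 85 is unaffected. Whether to count early terminators is a choice of estimand, and Step 4 puts the dilution at 2.5% to 5% under its assumptions.

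**A reader might further infer that urine biomarkers fall under two conflicting windows.** SAP 14.8.3 says several are measured in the 24-hour urine, and Table 2 seems to give that collection Days 64 to 91. The Week 12 row, however, appears to have lost a cell in the text as read. ECG ends its Week 6 window on Day 63, yet its Week 12 cell reads 71 to 91. Body weight ends its Week 8 window on Day 70, yet its Week 12 cell is blank although weight is taken at that visit. Moving those entries one column to the right gives ECG 64 to 91 and body weight 71 to 91, and both then follow on from the preceding windows. The 64 to 91 window therefore belongs to ECG, and no conflict for urine is shown.

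**Conclusion.** The gap is real and narrow. As written, subjects who cannot complete five stands leave the chair-stand ANCOVA because of their outcome, although the data needed to include them are collected. A true effect would tend to be understated by roughly 2% to 37%. Every input behind that range is assumed, and its upper end needs failure to be common already at baseline. With no true effect, the illustration shows essentially no bias.

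The failed-test gap concerns the chair stand only; KDQOL and the biomarkers are not affected by it. The endpoint lies outside the sequential testing of the primary and secondary endpoints, so no confirmatory conclusion changes. This is a cheap improvement to the plan.

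**What to change.** In SAP 14.7, keep the planned ANCOVA in seconds and add:

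1. An ANCOVA on ranks of the post-baseline result with the planned covariates. Subjects who attempted the test and could not complete it for a physical reason share the worst rank. Rank the baseline result by the same rule, so that a baseline failure does not remove the subject. Tests not done for other reasons stay missing.
2. A table of failed tests and their reasons by arm and visit.

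Specify before unblinding which recorded reasons count as physical.

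Optionally, add a supportive run of the chair stand, KDQOL and biomarker analyses limited to values near Day 85, with the day range stated in advance. The Table 2 window can stay as it is.

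The cost is SAP wording and programming on data already collected. The drawback is that a rank result cannot be read in seconds, which is why the two analyses should be shown together.
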